5. Treatment in the Study

In this study, patients were stratified based on initial clinical assessments into two primary categories: those designated for burr-hole drainage and those selected for conservative treatment. Each category was then subject to further randomization. Specifically, within the burr-hole drainage category, patients were allocated into either the 'burr-hole drainage + optimal medical care + MMA embolization' subgroup or the 'burr-hole drainage + optimal medical care' subgroup. Similarly, patients initially slated for conservative treatment were randomized into 'conservative management + optimal medical care + MMA embolization' and 'conservative management + optimal medical care' subgroups.

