6.4 Randomization

The assignment for each subject into either the control group (no MMA embolization) or the study group (MMA embolization) will be determined by the randomization scheme. SAS (version 9.4 or updated) is used to generate the randomization list by a stratified randomization method. During screening, a unique identification number (screening number) is allocated to each subject who has provided the signed ICF. The annotation for the screening number includes a subject number and site number (e.g., the first subject in 01 site is 01001). This digital ID is allocated according to the order of entry into the study after the subject signs the ICF at the study site.

On day 0 of the trial, subjects obtain the corresponding randomization numbers and will be randomized to the study group or the control group at a ratio of 1:1.

The randomization number of subjects in all study groups is designated as #: D-ZZZ

D = representing the treatment group; expressed with Arabic numerals 1-X, where 1 represents the study group and 2 represents the control group.

ZZZ=Subject digital ID

Treatment allocation in this study is not blinded.

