
 
Section 7.3.2 The analyses of secondary endpoints will be the same as those for the primary endpoint, and comparisons between groups will be made using the Chi-square test (qualitative measure) or t-test (quantitative measure). For event endpoints, the Kaplan Meier method will be used.
 
	
 
For two continuous secondary endpoints, Change of maximum hematoma thickness and hematoma volume between baseline and 90 days, a linear mixed effects model approach will be used to estimate the mean estimate (95% CI) of change from baseline for both treatment groups and mean estimate (95% CI) of difference between groups and p-value of difference between groups; Treatment group variables, sex, age, surgical treatment strata (trepanation/drainage vs. no trepanation/drainage), any usage of antiplatelet or anticoagulant therapy within one month before randomization(yes vs no), hematoma volume of baseline CT will be included in the model. The random effects will be site. For other continuous secondary endpoints, group comparisons will be performed using t-tests or Mann-Whitney U tests and 95% confidence intervals for
 
	
 
According to internal discussion as well as reference to the design of similar studies, secondary endpoints do not include time-to-event analyses and linear mixed effects model analysis methods are added.
 

Protocol	Statistical Analysis Plan	
Statistical description in the protocol	Statistical description in statistical analysis plan	Reason for change
	the difference in means between groups will be calculated using normal approximation.	

 
None
 
	
 
Section 8.2.1 The results of central imaging assessment analysis of CT/MRI examinations required for the determination of the subject's primary endpoint in this study will be presented in tables. Central image evaluation will be performed by the Independent Central Image Review Committee. Neurological symptoms and follow-up mRS scores were derived from OAC review data.
 
Section 9.3.2.1 CEC assessments for adverse events of special interest.
 
	
 
Added central imaging assessments (CT/MRI examinations), CEC assessments (adverse events of special interest), and clarified data sources.
 

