### 8.2.2. Analysis Methods

- The primary analysis will compare groups using the CMH chi-square test (the stratification factor is whether or not to perform trepanation/drainage was performed), summarize the 90-day recurrence (trepanation/drainage group) / progression rate (non-surgical group) for the MMA embolization group and the control group using the two-sided 95% CI (Clopper-Pearson method) and summarize the two-sided 95% CI for the difference in recurrence or progression rates between the two groups using the Miettinen-Nurminen method.
- Sensitivity analyses will use generalized linear mixed-effects model to calculate ORs and their 95% CIs for the comparison of recurrence or progression rates between the two arms, with group as fixed effect, site as random effect. Results of multivariable analysis will also be

presented, including treatment group, sex, age, surgical treatment strata (trepanation/drainage vs. no trepanation/drainage), any usage of antiplatelet or anticoagulant therapy, hematoma volume of baseline CT as covariates.

Enter Analysis Methods and Results Presentation

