### 9.1.2.2. Statistical Analysis Methods

- 360 days recurrence or progression of SDH after randomization will be analyzed in the same way as the primary endpoint (Section8.2.2)
- Ordinal logistic regression will be used for intergroup comparison of mRS scale scores at 90 and 360 days after randomization, with treatment group, sex, age, surgical treatment strata (trepanation/drainage vs. no trepanation/drainage), any usage of antiplatelet or anticoagulant therapy within one month before randomization(yes vs no), hematoma volume of baseline CT as covariates.
- Other categorical secondary endpoints will be analyzed in the same way as the primary endpoint **(Error! Reference source not found.Error! Reference source not found.Section)**

- The linear mixed effects model approach will be used to estimate the mean estimate (95% CI) and the mean estimate (95% CI) of the differences between groups as well as the P values of the differences between groups for the change in maximum hematoma thickness at 90 days after randomization compared to baseline and the change in hematoma volume at 90 days after randomization compared to baseline; Treatment group variables, sex, age, surgical treatment strata (trepanation/drainage vs. no trepanation/drainage), any usage of antiplatelet or anticoagulant therapy within one month before randomization(yes vs no), hematoma volume of baseline CT , visit variables, and visit by treatment group variable interactions will be included in the model and site as the random effect.
- For other continuous secondary endpoints, T tests will be used to compare groups, and 95% confidence intervals for the difference in means between groups will be calculated using normal approximation.

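### The t-test secondary endpoints (midline shift, EQ-5D-5L, hospital stay, re-hospitalizations, expenses) are compared without the drainage/conservative category within which patients are randomised, which costs precision wherever that category predicts the outcome

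*SAP*

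**What the plan says.** Protocol section 5 describes two categories formed before allocation: "patients were stratified based on initial clinical assessments into two primary categories: those designated for burr-hole drainage and those selected for conservative treatment". It continues: "Each category was then subject to further randomization". Protocol 6.4 says that SAS is used to "generate the randomization list by a stratified randomization method", but it names no factor and no block size.

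The SAP uses the category in three places:
- The primary CMH test (SAP 8.2.2), where "the stratification factor is whether or not to perform trepanation/drainage was performed".
- The ordinal model for mRS (SAP 9.1.2.2), whose covariates include "surgical treatment strata (trepanation/drainage vs. no trepanation/drainage), any usage of antiplatelet or anticoagulant therapy within one month before randomization(yes vs no").
- The linear mixed model for change in hematoma thickness and volume (SAP 9.1.2.2), with the same covariates.

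For the remaining continuous endpoints, SAP 9.1.2.2 says: "For other continuous secondary endpoints, T tests will be used to compare groups", with normal-approximation 95% intervals for the mean difference. The t-test sample code in SAP 9.1.2.3 has treatment group as its only class variable. SAP Table 1 words the same item differently: "group comparisons will be performed using t-tests or Mann-Whitney U tests and 95% confidence intervals for" the mean difference. Neither test is stratified, and no reason is given for leaving the category out.

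**The concern.** When arms are balanced within a prognostic category, the difference between categories cancels out of the treatment comparison. It adds nothing to the true sampling error. A two-sample t-test nevertheless leaves that variation in its estimated standard error. Without such balance, the variation is real noise in the unadjusted difference, and adjustment would remove it. Precision is lost in both cases.

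The category could well predict these outcomes. Stay and expenses include an operation in one category only. One listed indication for drainage (Protocol 5.2) involves midline shift, so baseline shift should differ between categories.

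The treatment of related endpoints is also uneven. SAP 1.2 places thickness, volume and midline shift under one residual-hematoma objective at the same visit, yet only the first two are adjusted. EQ-5D-5L supports the health-status objective; stay, re-hospitalizations and expenses are listed under the readmission objective.

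**Working it through.** **The plan's own figure.** The documents state a sample size only for the primary endpoint. With 12% against 5%, two-sided 5% and 90% power:

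n per arm = [1.96·√(2·0.085·0.915) + 1.2816·√(0.12·0.88 + 0.05·0.95)]² / 0.07² = 331.5, rounded up to 332.

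Then 332/0.92 = 360.9, rounded up to 361 per arm, or 722 in total. The figure reproduces and leaves 664 evaluable patients. No SD, effect or power is stated for any t-test endpoint.

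**Inputs for the loss.** Let q be the share drained and d the gap between category means in within-category SDs. The documents give neither. Assumed ranges: q = 0.5 to 0.8, d = 0.5 to 1.5.

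**Case 1: allocation balanced within category.**
- b = q(1−q)d²
- Ratio of the t-test standard error to the correct one: k = √(1+b)
- True size of the nominal 5% test: 2Φ(−1.96k)
- Power after adjustment when the t-test has 80%: Φ(0.8416 + 1.96k − 1.96)

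| q | d | b | k | True size | Adjusted power (t-test 80%) |
|---|---|---|---|---|---|
| 0.5 | 0.5 | 0.0625 | 1.031 | 4.3% | 81.6% |
| 0.8 | 0.5 | 0.04 | 1.020 | 4.6% | 81.1% |
| 0.5 | 1 | 0.25 | 1.118 | 2.8% | 85.8% |
| 0.8 | 1 | 0.16 | 1.077 | 3.5% | 84.0% |
| 0.5 | 1.5 | 0.5625 | 1.250 | 1.4% | 90.9% |
| 0.8 | 1.5 | 0.36 | 1.166 | 2.2% | 87.8% |

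Simulation with 664 evaluable patients, normal outcomes and an effect set for 90% power after adjustment agrees (20,000 null and 10,000 alternative replicates per scenario):

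| q | d | CI width ratio | Size, t-test vs adjusted | Power, t-test vs adjusted |
|---|---|---|---|---|
| 0.5 | 0.5 | 1.031 | 0.040 vs 0.047 | 89.0% vs 89.8% |
| 0.5 | 1 | 1.118 | 0.028 vs 0.050 | 84.9% vs 89.6% |
| 0.8 | 1 | 1.077 | 0.037 vs 0.053 | 87.3% vs 90.1% |
| 0.8 | 1.5 | 1.166 | 0.020 vs 0.048 | 83.1% vs 90.0% |

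**Case 2: simple randomisation inside each category.** The t-test is then correctly calibrated. At q = 0.65, d = 1.5 and n = 722, simulated size was 4.96%, against 1.65% under balance. Adjustment still gains power: Φ(2.80k − 1.96), which at k = 1.118 takes 80% to about 88%.

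**The case against.** **Balance is not documented.** The strongest counter-argument is that too-wide intervals and a size below 5% require balance within category, for example by blocks. Protocol section 5 and 6.4 imply this but do not specify it. The objection stands: under simple randomisation those two statements fall away, and only the loss of efficiency remains.

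**The size is assumed.** This also stands. Two features may narrow the gap: conservative patients in the embolization arm also have a procedure, and conservative patients who progress may be operated on.

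**The SAP could be read as adjusting these endpoints.** SAP 9.1.2.3 lists all continuous endpoints in one block, with a covariates input alongside both the mixed-model and the t-test code. However, SAP 9.1.2.2 confines the mixed model to thickness and volume, and the t-test code takes no covariate.

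**Subgroup analyses are planned.** Protocol 7.3.3 compares arms within burr-hole and medically managed patients for secondary outcomes. Those results avoid the between-category variation but do not supply an adjusted overall estimate.

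**Only secondary endpoints are involved.** They carry no power target, so this is an improvement rather than a flaw in validity.

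A reader might infer that every confidence interval here is certainly too wide, or that the claims on health status and readmission are seriously weakened. The documents support neither. The first depends on undocumented balance. For the second, a modest gap such as 0.5 SD, plausible for EQ-5D-5L, costs 1–2 points, and nothing in the documents sizes the effect on re-hospitalizations.

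**Conclusion.** The point holds as one of efficiency and consistency. Five continuous secondary endpoints are analysed without the category used for randomisation, and precision is lost wherever that category is prognostic. This is true under either form of allocation. Conservative tests and over-wide intervals follow only if allocation was balanced within category.

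Under balance and the assumed 50–80% drained, the standard error is overstated by 2–3% at a 0.5-SD gap, 8–12% at 1 SD and 17–25% at 1.5 SD. From 80% power, adjustment recovers 1–2, 4–6 and 8–11 points respectively. The larger gaps are most plausible for stay and expenses, but that is a judgement and not a figure in the documents.

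The planned comparison is neither biased nor anti-conservative, and the primary conclusion does not depend on it.

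**What to change.** In SAP 9.1.2.2 and 9.1.2.3, replace the t-test with a linear model that has treatment and the drainage/conservative category as fixed effects. Use robust standard errors for stay and expenses, which are likely to be skewed. Report the adjusted mean difference with its 95% confidence interval and p-value. Where Table 1 allows Mann-Whitney, use the van Elteren test stratified by the same category.

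Define the category as decided before randomisation, not as drainage later performed. This needs saying because SAP 8.2.2 mixes the two ideas and SAP 1.2 refers to patients who undergo drainage.

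The cost is a change of wording and a short change of code. The target remains a difference in means. No new data should be needed, since Protocol 3.1 and section 5 place the decision before allocation. The visit schedule lists no separate item for it, so the team should confirm that the planned category is held as a variable. Stating in the SAP how allocation was balanced within category would settle which of the two cases applies.

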### 9.1.2.3. Model Specifications

Statistical analysis of binary categorical variables
Endpoints and parameters

 
● Endpoint: Change of mRS scale score at 90 and 360 days after randomization compared to baseline
 
● Parameters: 
 
– Ordinal OR and 95% CI
 
 
 

Input Variables

 
● AVAL: response variable
 
● TRTAN: groups
 
● SITEID: subject site number
 
● COUNT: number of subjects per level per group
 
● COVARIATES: adjusted Variables
 

SAS Code Sample

Logistic Regression Example Code:
 <pre>proc glimmix data=adeff descending;   class siteid trtan;   model aval/ count = trtan covariates / solution;</pre>

random intercept / subject= siteid; run;
Presentation of Results

 
The OR and 95% CI for the ratio can be obtained from Odds Ratio Estimates.
 

Statistical analysis of continuous variables
Endpoints and parameters

 
Endpoint: 
 
Changes of hematoma thickness in CT or MRI imaging at 90 days after randomization compared to baseline
 
Changes of hematoma volume at 90 days after randomization compared to baseline
 
Changes of midline shift in CT or MRI imaging at 90 days after randomization compared to baseline
 
Quality of life evaluated with EQ-5D-5L Scale at 90 days and 360 days after randomization compared to baseline
 
Total hospital stay (number of days)
 
Re-hospitalization times
 
Total hospitalization expenses
 
 
 
Parameters: 
 
Mean and 95% CI
 
Difference in means and 95% CI with P-value
 
 
 

Input Variables

 
AVAL: response variable
 
TRTAN: group
 
SITEID: subject site number
 
AVISITN: visit variables
 
COVARIATES: adjusted variables
 

SAS Code Sample

Linear Mixed Effects Model Method Example Code:
 <pre>proc mixed data = adeff; class trtan siteid avisitn; model aval = trtan covariates avisitn avisitn avisitn trtan/solution ddfm = kr; random siteid /type = cs; lsmeans trtanavisitn/diff cl alpha = 0.05 e; ods output lsmeans = lsmeans diff = diff; run;</pre>

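### The SAP promises an ordinal odds ratio for mRS, but the sample code beneath it fits a binomial events/trials model and cannot produce one

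*SAP*

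**What the plan says.** The method text in SAP 9.1.2.2 is clear about the type of model: "Ordinal logistic regression will be used for intergroup comparison of mRS scale scores at 90 and 360 days after randomization". It lists treatment group, sex, age, surgical stratum, antithrombotic use and baseline hematoma volume as covariates. It does not mention site for this endpoint.

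The specification in SAP 9.1.2.3 reads differently:

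- The block is headed "Statistical analysis of binary categorical variables".
- The response is a change score: "Endpoint: Change of mRS scale score at 90 and 360 days after randomization compared to baseline".
- The parameter is ordinal: "Ordinal OR and 95% CI".
- The inputs include "COUNT: number of subjects per level per group".
- The procedure call is "proc glimmix data=adeff descending" and the model statement is "model aval/ count = trtan covariates / solution", followed by a random intercept for site.
- For the result, the reader is told: "The OR and 95% CI for the ratio can be obtained from Odds Ratio Estimates".

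The model line is the same as the one in SAP 8.2.3.2 for the binary sensitivity analysis of the primary endpoint. The SAP gives no other code for an ordinal model.

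**The concern.** In PROC GLIMMIX, a response written as one variable over another is events/trials syntax and, with no distribution named, gives a binomial logit. That is standard behaviour of the procedure; the SAP does not state it. Such a model has one intercept and no cumulative logits, so its treatment coefficient is not a common odds ratio across mRS levels. The denominator is also wrong: COUNT is a cell frequency, not a number of trials. The block looks like the binary template reused without adapting it to an ordinal response.

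At stake is the estimate for a named secondary objective, improvement in clinical outcome by mRS at 90 and 360 days. If the code were run as printed, the reported odds ratio would not measure that outcome. If the programmer departed from it, the model would be chosen after the plan was fixed.

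**Working it through.** **The plan's own figure.** Protocol 7.1.3 gives 5% against 12%, two-sided alpha 0.05, power 90% and 8% loss. With pooled variance under the null and no continuity correction:

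n = [1.960 × √(2 × 0.085 × 0.915) + 1.282 × √(0.12 × 0.88 + 0.05 × 0.95)]² / 0.07² ≈ 331.5, so 332 per arm.

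332 / 0.92 = 360.9, so 361 per arm and 722 in total. The figure reproduces and does not involve mRS. The SAP states no power for mRS.

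**The code with COUNT as defined (per level per group).** The data then have one row per mRS level and arm. Protocol Appendix 3 lists levels 0 to 5. A binomial logit with treatment as the only term fits, in each arm, total events over total trials.

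- Events per arm: 0 + 1 + 2 + 3 + 4 + 5 = 15, however patients are spread over the levels.
- Trials per arm: the arm size, say 361.
- Odds per arm: 15 / (361 − 15) = 15/346.
- Odds ratio: (15/346) / (15/346) = 1.00.

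For unequal arms of size N0 (control) and N1 (embolization) it becomes (N0 − 15) / (N1 − 15). That reflects arm size, not outcome.

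**Check on constructed data.** These inputs are assumed and not in the documents: levels 0 to 6, control distribution 40/25/15/8/5/3/4%, about 332 per arm, proportional odds, no covariates or site effect. Events per arm now sum to 21 when all rows are valid.

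| True common OR | Cumulative logit | Code as written |
|---|---|---|
| 1.5 | 1.50 | 1.00 |
| 2.0 | 2.00 | 1.00 |
| 3.0 | 2.98 | 0.47 |

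In the last row the embolization arm has 4 patients at level 5 and 5 at level 6, so events exceed trials in both rows and they are excluded. That leaves 10 events in 323 trials against 21 in 333: (10/313) / (21/312) = 0.47. The estimate moved because two rows became invalid, not because the model recovered the effect.

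**Change in mRS as the response.** SAP 9.1.2.1 defines change as follow-up minus baseline. A patient who improves has a negative value, which cannot be an event count.

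**Other data layouts.** The site intercept and the patient-level covariates need finer cells than COUNT as defined. Any cell whose score exceeds its count is then invalid. The loss depends on the layout, which the SAP does not fix. As a range, assume mRS 0 to 5 probabilities of .20/.35/.20/.12/.08/.05 (control) and .28/.37/.17/.10/.05/.03 (embolization):

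- *Per level per group:* the smallest expected cell at 361 per arm is 0.03 × 361 = 10.8, against a score of 5, so essentially nothing is lost.
- *One patient per cell:* every score of 2 or more is invalid, which removes 45% of controls (.20 + .12 + .08 + .05) and 35% of embolization patients (.17 + .10 + .05 + .03).
- *Cells by site:* the loss falls between these.

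**The case against.** The best defence is that this is sample code. It is labelled as an example, it contains a placeholder for covariates, and both the method text and the target parameter are ordinal. A competent programmer would follow those. The mRS 0–2 and 0–3 proportions do not depend on this block either.

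That limits the importance of the point but does not remove it. The text cannot simply override the code, because the two sections also disagree on the response (score or change) and on site (absent or a random intercept), and SAP Table 6 lists change in mRS as both categorical and continuous. Nor is this a text-extraction loss: the statement closes immediately after its single option, and the code requests no odds-ratio output although results are to be read from such a table.

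Some stronger readings are not supported:

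- *That the code discards mainly the worst-outcome patients, or some fixed large share of cells.* This needs site-level or patient-level cells. With COUNT as documented, almost no cell is lost. For change scores, it is the patients who improve who become invalid.
- *That mRS is the main secondary endpoint.* Neither document ranks the secondary endpoints.
- *That the primary result is affected because SAP 8.2.3.2 has the same line.* The primary test is the CMH chi-square. The GLIMMIX model there is a sensitivity analysis of a binary outcome, for which a binomial family is the right type.

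**Conclusion.** The point stands as an error in the example code for a secondary endpoint. Run as written, the code cannot give the ordinal odds ratio that the SAP promises. The result of exactly 1.00 rests on COUNT as defined, equal arms, all levels occupied, and no covariates or site effect. Under other layouts the output changes, but in none is it a cumulative odds ratio. How many records would be lost cannot be determined from the documents. They also do not show which program was finally run, so this is a fault in the plan and not evidence that any reported mRS result is wrong.

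**What to change.** In SAP 9.1.2.3:

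1. Use one record per patient, with `model aval = trtan covariates / dist=multinomial link=cumlogit oddsratio solution;`. Remove `/count` and drop COUNT from the inputs, or keep COUNT only as a frequency variable.
2. Change the block heading from binary to ordinal.
3. Reconcile 9.1.2.2 and 9.1.2.3 on whether the response is the mRS score or its change from baseline.
4. Reconcile the same sections on whether site is a random effect; if so, keep the random intercept and say so in 9.1.2.2.

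The cost is a code correction and a short clarification. No design figure, data collection or primary analysis changes.

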Each subject participating in the study must have a complete eCRF, and each page in the form must be reviewed and approved by the PI. The PI will confirm that he/she has reviewed the recorded data by electronic signature in the electronic data collection page. The PI may entrust the review and confirmation to a qualified doctor who may be appointed as an assistant investigator. Investigators must keep a copy of the eCRF, including records of changes and corrections.

11.4 Data and Safety Monitoring Board: An independent Data and Safety Monitoring Board (DSMB) will be established to regularly review and analyze all safety data. The effect data generated by the study will be evaluated by DSMB for potential risks and benefits of the treatment. DSMB will be composed of independent professional doctors (at least 2 persons) who will not undertake the recruitment of subjects in this study and a biostatistician whose identity is not disclosed. DSMB will keep SAEs under review. DSMB will review the frequency and severity of all aEs as well as demographic data, etc. Specific meetings may be held for any safety reasons during the study. Based on results of data review, if any termination criterion is met, DSMB will give suggestions on whether to continue, adjust or terminate the study. Other responsibilities and details of DSMB will be included in the DSMB Charter.

11.5 Clinical Event Committee (CEC): The CEC will independently and impartially evaluate the safety events, including at least all protocol-specified safety endpoints of the subjects. The CEC should be composed of at least three independent physicians, one of whom will act as CEC President. Details regarding the responsibilities of CEC

members and clinical events that require CEC review will be included in the CEC constitution.

- 11.6 **Imaging assessment committee (IAC):** The primary and secondary endpoints of the trial involve quantitative imaging assessments, which will be reviewed by the IAC with data including at least: CT/MRI (screening period/baseline, 90-day follow up [V4], 360-day follow up [V5]), and DSA imaging (target vessels [MMA main and branch vessels]).
- 11.7 **Outcome Assessment Committee (OAC):** The OAC is responsible for evaluation of multiple subjective data, including at least clinical symptoms and mRS score (90-day follow up [V4] and 360-day follow up [V5]).

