## 2. Statistical Hypothesis

Hypothesis testing will be performed on hematoma recurrence or progression rates.

- Null hypothesis: there is no difference in the incidence of recurrence or progression of hematoma between the MMA embolization group and the control group at 90 days after randomization;

- Alternative hypothesis: there is difference in the incidence of recurrence or progression of hematoma between the MMA embolization group and the control group at 90 days after randomization.

The above hypothesis tests will be two-sided and statistical significance will be determined as a p-value of  $<0.05$ , and two-sided 95% confidence intervals will be reported.

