**Presentation of Results**

Linear mixed effects model approach:

- Estimation of mean and 95% CI for both groups:
  - Point Estimate: Estimate Variable in lsmeans dataset
  - Corresponding 95% CI: Lower vs. Upper variables in lsmeans dataset
- Estimate and 95% CI for difference in means between groups:
  - Filtered all TRT A N ≠ TRT A N and AVISITN = AVISITN records in Diffs dataset and output:
    - Point Estimate: Estimate Variable in Diffs Post-Screening Dataset
    - Corresponding 95% CI: Lower versus Upper Variables in Diffs Post-Screening Dataset
- P-value: Probt variable in filtered dataset Diffs

T-Test:

- The difference in means and 95% CI are available from CONFLIMITS.
- P-values for t-tests are available from TTESTS.

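### The hematoma mixed model has visit terms but no patient-level covariance; if day-360 scans enter, the day-90 standard error is right only when the residual SDs at the two visits are about equal

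*SAP*

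**What the plan says.** The SAP describes this model in three places.

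- **SAP 9.1.2.2 (methods text).** For change in maximum thickness and change in volume at 90 days, after the baseline covariates, it says "visit variables, and visit by treatment group variable interactions will be included in the model and site as the random effect".
- **SAP 9.1.2.3 (sample code).** The classification line is "class trtan siteid avisitn" and the random statement is "random siteid /type = cs". There is no REPEATED statement, and no patient identifier appears in the code or among the listed input variables. The compound-symmetry option acts on the site effect, so it does not describe scans within a patient. Under Presentation of Results, the between-arm differences are picked out by matching visit: "AVISITN = AVISITN records in Diffs dataset and output".
- **SAP Table 1.** The same two endpoints get a linear mixed model with the same covariates and "The random effects will be site", but no visit terms.

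The endpoint itself is a single time point, for example "Changes of hematoma volume at 90 days after randomization compared to baseline". Central imaging review, however, covers "CT/MRI (screening period/baseline, 90-day follow up [V4], 360-day follow up [V5" (Protocol 11.6), and the SAP Appendix 1 flow chart also schedules CT/MRI at V4 and V5. A patient can therefore contribute two post-baseline change values. The SAP does not say which visits enter the model.

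**The concern.** Visit and visit-by-treatment effects can be estimated only from at least two visits, and filtering the differences by visit has a purpose only if there are several. A programmer following 9.1.2.2 and 9.1.2.3 would probably stack the day-90 and day-360 rows. The fitted model would then hold two assumptions that the SAP neither states nor justifies:

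- two scans of one patient are no more alike than scans of two different patients at the same site;
- the residual variance is the same at day 90 and day 360.

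The day-90 comparison would take its standard error from a variance pooled over both visits. This model supplies the confidence intervals and p-values for the two imaging endpoints that serve the residual-hematoma objective. It also could not use a patient's own day-360 scan to inform a missing day-90 value, which is the usual reason for a repeated-measures model.

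**Working it through.** **The plan's own figure.** The documents give no SD, correlation or power for hematoma thickness or volume. The only design figure is the primary-endpoint sample size. With 12% versus 5%, two-sided 5% alpha and 90% power (pooled variance, no continuity correction):

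n per arm = [1.96·√(2·0.085·0.915) + 1.2816·√(0.12·0.88 + 0.05·0.95)]² / 0.07² = 331.5, rounded up to 332.

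The total is 664, and 664/0.92 = 722, which matches. The 664 is used below only as the number of evaluable patients in a simulation.

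**Inputs.** From the SAP: the model terms quoted above, and the rule in section 2 that "two-sided 95% confidence intervals will be reported". Assumed, because the documents are silent:

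- r = SD of the day-360 change divided by SD of the day-90 change (residual SDs, after covariates and site);
- f = share of patients with a day-360 scan.

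**Formula.** With full treatment-by-visit terms, the day-90 difference is in essence the difference in day-90 arm means. Its true variance is s90²(1/n1 + 1/n0). The model replaces s90² with the pooled value (s90² + f·s360²)/(1 + f). Hence

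model SE / true SE = √[(1 + f·r²)/(1 + f)], and coverage = 2Φ(1.96 × ratio) − 1.

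Example with r = 0.5 and f = 1: √(1.25/2) = 0.791, and 2Φ(1.550) − 1 = 87.9%.

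| r (assumed) | SE ratio, f = 1 | Coverage, f = 1 | SE ratio, f = 0.85 | Coverage, f = 0.85 |
|---|---|---|---|---|
| 0.5 | 0.791 | 87.9% | 0.810 | 88.7% |
| 0.75 | 0.884 | 91.7% | 0.894 | 92.0% |
| 1 | 1.000 | 95.0% | 1.000 | 95.0% |
| 1.25 | 1.132 | 97.4% | 1.122 | 97.2% |
| 1.5 | 1.275 | 98.8% | 1.255 | 98.6% |

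The rejection rate under no difference is 100% minus coverage: about 12% at r = 0.5 and about 1% at r = 1.5, with f = 1.

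**Simulation check.** Settings: 664 patients, 33 sites (the protocol plans 30 to 40), complete data at both visits, 3,000 runs per setting, fixed site intercepts standing in for the random site effect. Coverage for within-patient correlations of 0, 0.3 and 0.7 was:

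- r = 0.5: 86.9%, 89.3%, 88.2%
- r = 0.75: 92.5%, 92.6%, 90.1%
- r = 1: 95.1%, 94.7%, 94.3%
- r = 1.5: 98.8%, 98.4%, 98.5%

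At a fixed r, the correlation moves coverage by at most about 2.5 points. Some of that is simulation noise: at 90% coverage the Monte Carlo standard error is √(0.9·0.1/3000) = 0.55 points. The common variance is the main source of error in the day-90 interval.

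**Day-90 rows only.** The intercept, treatment, visit and interaction columns then have rank 2 out of 4. The visit terms drop out and no repeated-measures problem remains.

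**The case against.** The strongest reply is that the SAP never says day-360 rows enter this model. Every statement of the thickness and volume endpoints is for day 90, the day-360 CT also serves the 360-day recurrence or progression endpoint, and Table 1 has no visit terms. This stands in part: the defect is conditional. It does not remove the point, because 9.1.2.2, the code and the visit filter all suggest several visits, and on the other reading the SAP contains terms that cannot be estimated.

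A second reply is that the code is labelled as an example. That carries little weight, because the prose in 9.1.2.2 also names site as the only random effect and no within-patient covariance is given anywhere.

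A reader might go further and infer that the day-90 interval is too narrow, on the ground that most hematomas have resolved by day 360 and vary little by then. The documents do not support this. The outcome is change from baseline, so after full resolution the change equals minus the baseline value and keeps the baseline spread. The model adjusts for baseline volume, not baseline thickness, so for thickness only part of that spread is removed. An illustration with assumed values: volume-adjusted baseline thickness SD 6 mm, day-90 thickness SD 4 mm, full resolution at day 360.

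- Baseline to day-90 correlation 0: r = 6/√(36 + 16) = 0.83, coverage about 93%.
- Correlation 0.4: r = 6/√(36 + 16 − 19.2) = 1.05, interval slightly too wide.

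The argument is more plausible for volume, whose baseline value is a covariate, but no volume SD is given either.

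A reader might also blame ignored correlation or inflated degrees of freedom. With complete data the first adds little to the day-90 contrast, and the second is immaterial at about 664 patients. Correlation matters more for visit-to-visit contrasts, covariate standard errors and patients missing one scan.

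**Conclusion.** The concern holds conditionally. SAP Table 1 and SAP 9.1.2.2 and 9.1.2.3 describe different models for the same two endpoints. If both follow-up visits enter, the version with visit terms is misspecified as a repeated-measures model. Its day-90 standard error is too small if the day-360 change varies less than the day-90 change, and too large if it varies more. Over the assumed SD ratios of 0.5 to 1.5 with every patient scanned at day 360, it is 0.79 to 1.27 times the true value, with coverage of about 88% to 99%. These figures show a range and are not predictions, since the SD ratio, the within-patient correlation and the share scanned at day 360 are all assumptions.

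The consequence is limited to change in hematoma thickness and volume, which stand in an unranked list of secondary endpoints. The primary analysis does not use this model, so nothing here bears on the main conclusion of the trial. The correction is still worth making, because the plan as written supports the standard error only by coincidence of equal SDs.

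**What to change.** State in SAP 9.1.2.2 which visits enter the thickness and volume model, and make Table 1, 9.1.2.2 and 9.1.2.3 agree. Then choose one of two specifications.

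(a) **Keep both visits.** Add `usubjid` to the CLASS line and to the input variables, add `repeated avisitn / subject=usubjid type=un;`, keep site as a plain random effect without the TYPE option, and report the day-90 contrast. Each visit then has its own variance, and a patient's day-360 scan can inform a missing day-90 value.

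(b) **Fit day-90 data alone.** Drop the visit and visit-by-treatment terms and the visit filter. This is simpler, but gives up the day-360 scans of patients who miss the day-90 scan.

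Either choice removes the pooled-variance error: the standard-error ratio becomes 1.00 and nominal coverage 95%. The cost is a few lines of SAP text and code. No new data are needed.
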